5. STUDY TREATMENT

5.1 Chinese herbs Formulation, Packaging, and Handling:

Chinese herbs for study formula (**Shu Yu Wan**) will be imported from Sun Ten Pharmaceutical Company in Taiwan and will be manufactured as a sachets and capsules by BEMA Botanicals distribution company in Vancouver. As described above BEMA have in place processes for certifying sourcing of herbs and verification of absence of contaminants and complies with Health Canada's Good Manufacturing Practices. BEMA will compound the capsules and sachets (<http://www.bemabotanicals.com/>). The signed copy of certificate of analysis (COA) provided by Bema's supplier will be kept with BEMA. The BEMA Botanicals obliged periodically inspect the cultivation site and analyze the samples to ensure they are fresh and not sulfur fumigated.

BEMA's quality assurance department also will keep a copy together with all batch manufacturing records. All the basic testing such as heavy metals, microbiological test, etc. is conducted by SUNTEN's quality assurance department.

Study of Chinese herbs and lung cancer patients
Principal Investigator: [name]

The formula will be shipped in light opaque-white HDPE jars that contain an estimated 500 caps/sachets to the Peter Brojde Lung Cancer Clinic in Montreal by UPS (about 3 days), and stored at room temperature.

Table 2 Study formula - Shu Yu Wan (*Chinese Yam Pill*)

	Ingredients	Ratio	Percent	Daily dose (mg)
1	RenShen (Radix et Rizoma Ginseng)	7	3.5%	350
2	Bai Zhu (Rhizoma Atractylodis)	6	3.0%	300
3	Fu Ling (Poriae)	5	2.5%	250
4	Zhi Gan Cao (Radix GlycyrrhizaPreparata)	20	10.0%	1000
5	Shu Di Huang (Rehmannia glutinosa)	10	5.0%	500
6	Bai Shao (Radix Paeoniae Alba)	6	3.0%	300
7	Dang Gui (Radix Angelica sinensis)	10	5.0%	500
8	ChuanXiong (Rhizoma Chuang xiong)	6	3.0%	300
9	Gui Zhi (Ramulus Cinnamomum)	10	5.0%	500
10	Xing Ren (Semen armeniaca amarum)	6	3.0%	300
11	JieGeng (RadixPlatycodonis)	5	2.5%	250
12	Fang Feng (Radix Saponikoviae)	6	3.0%	300
13	Da Zao (Fructus Jujubae)	5	2.5%	250
14	ShenQu (Massa Medica Fermentata)	10	5.0%	500
15	Dong Chong Xia Cao (Cordyceps)	10	5.0%	500
16	Shan Yao (RhizomaDioscoreae)	30	15.0%	1500
17	Mai Men Dong (Radix Ophiopogonis)	6	3.0%	300
18	Chai Hu (Radix Bupleuri)	5	2.5%	250
19	E Jiao (Colla Corii asini)	7	3.5%	350
20	Bai Bian Dou (Semen Lablab Album)	10	5.0%	500
21	Gan Jiang (Rhizoma Zingiberis)	3	1.5%	150
22	Ling Zhi (Ganoderma)	10	5.0%	500
23	Hong ZhingTian (Rhodiola crenulatae)	7	3.5%	350

	Total	200	100	10g
--	--------------	-----	-----	-----

5.2 Study assessments

Flowcharts of scheduled study assessments are provided in Table 3. Patients will be closely monitored for safety and tolerability throughout the study. At each visit patients will be asked about new or worsening of existing symptoms. The severity of the adverse reaction will be determined by Common Terminology Criteria for Adverse Events (CTC AE) version 3.0. All assessments must be performed and documented for each patient in the CRF.

5.3 Medical History and Demographic Data

Medical history includes clinically significant diseases, surgeries, cancer history (including prior cancer therapies and procedures), reproductive status, smoking history, use of alcohol and drugs of abuse, and all medications (e.g., prescription drugs, over-the-counter drugs, herbal or homeopathic remedies, nutritional supplements) used by the patient within 7 days prior to the screening visit. Demographic data will include age, sex, and self-reported race/ethnicity.

5.4 Patient-Reported Outcomes

Symptoms and health status will be assessed using the Functional Assessment of Cancer Therapy-lung (FACT-L) and ESAS, (Edmonton Symptom Assessment System)(Appendix 3). The FACT-L is a 36-item self-report questionnaire that evaluates quality of life in lung cancer patients [77, 78]. Twenty-nine items measure physical, social, emotional and functional well-being; The final 7 items constitute the Lung Cancer Symptom Scale (LCSS)[79].

The questionnaires, available in French and English, will be distributed by the staff and completed by the patient. The questionnaire(s) will be completed on Day 1 (prior to any other discussions with study personnel) and at each visit (every 2 weeks) until study completion at 6 weeks. Study personnel will review all questionnaires for completeness before the patient leaves the investigational site, and the hard copy originals of the questionnaires will be kept in the patient's research record for data verification.

Table 3 Schedule of Assessments

Table 3 Schedule of Assessments

	Screening visit	Visit 1 (0)	Visit 2 (2 wks)	Visit 3 (4 wks)	Study end (6wks)
Written Consent	+				
Medical history (including other medical conditions, cancer type and stage and all medications)	+				
Update medical history and verify all medication		+	+	+	+
Blood test as per standard of care	+	+	+	+	+
INR test			+		+
Physical exam as per standard of care	+	+	+	+	+
Vital signs	+	+	+	+	+
Height	+	+			+
Weight	+	+	+	+	+
Karnofsky performance status	+	+	+	+	+
CT chest as per standard of practice					
Revised Edmonton Symptom Assessment System		+	+	+	+
FACT-L		+	+	+	+
Chinese herbs Dispensed		+	+	+	
Diary Returned/Dispensed		+	+	+	+
End of study acceptability questionnaire					+

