1.3 Clinical Safety of Chinese herbs

There are many areas of uncertainty and legitimate concern in trying to predict the potential toxicity of CH formulas such as the one proposed in clinical populations. We have identified the following general types of concerns and have addressed each one as it pertains to the proposed CH study at the Peter Brojde Lung Cancer Centre below:

- A. The inherent variability in chemical composition of herbs due to cultivation conditions and different geographic sources. **Response:** The source company for the herbs in this study (BEMA) obtain their botanicals from reputable farms in Taiwan (San Ten Pharmaceutical Company) and the Certificate of Analysis are provided (Appendix 1)
- B. The possibility of contamination with undeclared potentially toxic ingredients including heavy metals (arsenic, cadmium, lead and mercury) or microbial contamination (e.g. *E. coli*, *Salmonellaspp*, *Staphylococcus aureus*). **Response:** Each component has been independently tested at San Ten pharmaceuticals to confirm purity and absence of contamination and certificates confirming this are attached (Appendix 2)
- C. The difficulty accurately predicting safety and efficacy of individual ingredients from CH when the only robust quantitative data available is from pre-clinical experiments using doses that are frequently far higher than those achievable in humans. **Response:** The components of the CH formula we plan to use have been used for therapeutic benefit for several hundred years, and continue to be used to treat cancer patients in China. Community studies of reported side-effects from over-the-counter i.e. unsupervised, CH use [66] most commonly (<10%) include minor side effects such as allergic reactions (e.g. erythema, itching), dizziness and gastro-intestinal symptoms (e.g. diarrhea, stomach ache and cramping). Other rare (<1%) reported side-effects of individual herbs at very high doses include: several weeks or months' use of higher doses (e.g. >600 mg/day) of Licorice can cause suppression of the renin-aldosterone axis

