leading to hypertension and hypokalemia [67]; Increased risk of bleeding: dong quai (angelica senesis) at the dose of 4.5 g daily due to antiplatelet activity: concurrent use of anticoagulants is not recommended [68]; Neurological and psychiatric toxicity: Panax ginseng may cause insomnia, mania and/or euphoria when used in a dose >2 g daily over prolonged time (3 months) [69, 70]. The toxicities reported argue for supervised use of CH in clinical studies to monitor symptoms and parameters such as blood pressure.

D. There is genuine difficulty in predicting potential clinically important interactions between CH and other chemicals or biomolecules at physiologically relevant concentrations. This in turn raises the possibility that for patients receiving potentially highly toxic treatments such as chemotherapy, CH may increase the risk of toxicity. Additionally, for patients being treated with curative intent there is potential that any additional treatment such as CH may reduce rather than enhance any anti-cancer effect and jeopardise survival. **Response:** In recent years there has been a rapid increase in the number of published studies using CH in cancer patients, including many studies using CH at the same time as chemotherapy. Not one of these studies has reported an increase in symptoms or adverse effects due to CH despite use in a variety of different patient groups, and many claim that CH enhances rather than reduces anti-cancer treatment effects. This protocol is deliberately designed to test CH in stage IV lung cancer patients, where anti-cancer treatment is intended to reduce or control symptoms and improve quality rather than extend life. To be able to better identify if CH are causing, rather than reducing toxicity for those on chemotherapy, we will start CH only in patients who have no chemotherapy planned or in those starting chemotherapy CH will be initiated only if they are clinically stable and have completed at least the first cycle of chemotherapy. Furthermore, to reduce the potential for other toxicities, patients will be instructed not to take other over-the-counter CH.

1.4 Rationale, composition and safety data for the of the study formula - Shu Yu Wan (Chinese Yam Pill) formula

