All the components of the modified **Shu Yu Wan in this protocol** have been approved by Health Canada and listed as acceptable medical ingredients[71, 72], and were the subject of in-depth analysis process as part of a prior CIHR grant application to determine efficacy and safety of CH in cancer patients [73]. Although some mild side effects have been reported when single herbs from the **Shu Yu Wan formula** have been used in doses far exceeding that in our formula, none of the component of this formula are listed as a herbals to be used with caution in *Herb Contraindications and Drug Interactions, 4th edition*[74]. Furthermore most of the ingredients have a high therapeutic index and are unlikely to cause toxicity even used in considerable excess. In general, use of combinations of smaller quantities of herbs seems to cause fewer adverse reactions than larger doses of single herbs, and

combining 23 herbs in one formula allows the use of smaller doses of herbs with synergistic beneficial effects.

More details of individual potential herbal-drug interactions of the components the modified Shu Yu Wan formula is presented in the Appendix 3. It should be noted that most of the data on toxicities reported here come from studies cited in Chinese Herbology textbooks [75].

The closely related modified Shu Yu Wan formula used in another study of advanced lung cancer patient receiving chemotherapy led to significantly fewer adverse reaction when compared to chemotherapy alone [49]. However we note that most of the herbs are metabolized in the liver and that there is potential for reversible hepatotoxicity at high doses or in susceptible patients [76]. This general point will be taken into account in patient selection for the current study. Thus, we propose to exclude patients with abnormal liver function or those taking drugs with long half-lives namely anti-convulsants, anticoagulants, or lithium where minor changes in drug metabolism may lead to delayed and potentially serious sequelae.

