2. OBJECTIVES

2.1 Primary objectives:

- To assess the acceptability and feasibility of conducting a 6-week intervention with a standard CH formula designed to treat symptoms commonly experienced by patients with advanced NSCLC.

Acceptability will be assessed using the following questions at the end of the study:

- **Indirectly** from adherence and feasibility (see below)
- **Directly** from responses to the following questions:
 - i) “*Was the Chinese Herb treatment used in this study easy to take?*” Yes / No
 - ii) “*If you experienced any problems or side effects taking the Chinese Herb treatment used in this study, please tell us what these were.*” (Free text)
 - iii) “*If it was available, would you be willing to take the Chinese Herb treatment used in this study again?*” Yes / No / Don’t know

Feasibility will be assessed using the following indices:

- Willingness to participate: proportion of subjects enrolled from number of patients approached .
- Completion rates: proportion of enrolled subjects who completed study (including final assessment) (threshold for positive study: 60%)
- Adherence rates: Proportion of doses taken of number prescribed (threshold for positive study: 66%)

2.2 Secondary objectives:

- a) Assess the magnitude of the patients' quality of life response and symptoms change after the 6 -week intervention compared to baseline.
- b) Estimate an appropriate sample size for the fully implemented study

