4.4 Method of Treatment

After written informed consent has been obtained and eligibility has been established the patient will be asked to complete FACT-L and ESAS questionnaires. The patients will be offered the choice of taking the CH formula in capsules or sachets and given instructions about recommendations to improve palatability. The formula should be taken with meals 3 times a day (each dose is either 1 sachet or 4 capsules) for six-weeks. Patient will be instructed to complete a diary each day to confirm adherence to treatment and to indicate the reason(s) that any doses were missed or treatment was stopped. A two-week supply of the CH capsules/sachets will be dispensed to patient at the start of the study. Every two weeks thereafter diaries will be collected/checked with the patient and a new diary dispensed with the next two-week supply of formula. The written instructions about dosage, frequency, dosage timing and what to do in the event of an adverse reaction will be given to patients.

Study of Chinese herbs and lung cancer patients

Principal Investigator: [name]

Patients will be allowed to maintain their concomitant medications during the trial with exception of over-the-counter herbal supplements.

4.5 Withdrawal.

Patients may withdraw at any time during the trial for the following reasons:

1. Patient no longer wishes to participate
2. The patient's doctor makes the decision to withdraw the patient if any side effects are suspected.
3. An allergic response or adverse reaction to the Chinese herbs
4. A change in clinical status necessitating emergency admission for treatment
5. Evidence of worsening liver function or need to start medication included in the exclusion criteria.
6. Reduction of chemotherapy dose due to Grade 3 toxicity

In case if participation terminated prematurely, patient will still be asked to attend for the end of the study visit.

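### Table 2 doses licorice above the level that Section 1.3 links to hypertension and hypokalemia (if both figures share a basis), and the protocol requires no potassium test

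*Protocol*

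**What the plan says.** Four parts of the protocol bear on this point.

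- **Hazard (Section 1.3, item C).** Among rare (<1%) effects of individual herbs at very high doses, the protocol states that "higher doses (e.g. >600 mg/day) of Licorice can cause suppression of the renin-aldosterone axis", "leading to hypertension and hypokalemia", after weeks to months of use. It gives dose levels for two other herbs: dong quai at 4.5 g daily (bleeding) and ginseng above 2 g daily (neuropsychiatric effects). It concludes: "The toxicities reported argue for supervised use of CH in clinical studies to monitor symptoms and parameters such as blood pressure".
- **Dose (Section 5.1, Table 2, row 4; Section 4.4).** Zhi Gan Cao, "Radix GlycyrrhizaPreparata", which is licorice root, makes up 10.0% of a 10 g daily total, or 1000 mg/day. It is taken for six weeks.
- **Reassurance (Section 1.4).** The protocol concedes some mild side effects where single herbs "have been used in doses far exceeding that in our formula".
- **Monitoring (Section 5.4, Table 3).** Vital signs are marked at all five visits. So is the row "Blood test as per standard of care", which lists no analytes. INR, at weeks 2 and 6, is the only laboratory test named. The one withdrawal reason in Section 4.5 that points to a blood result is "Evidence of worsening liver function or need to start medication included in the exclusion criteria".

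**The concern.** The protocol names a hazard, gives a dose and duration for it, and then prescribes a larger dose of the same herb for a period within that duration, while describing the hazard as one of very high doses. Someone reading the safety rationale alone, such as an ethics board member or a treating physician, could take licorice to be dosed well below any reported effect.

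The monitoring follows only half of the hazard. A rise in blood pressure would presumably be seen in the vital signs. A fall in potassium without symptoms would be seen only if the usual blood panel happens to include potassium. Asking about symptoms at each visit would not reveal it. Participant safety and the accuracy of the safety rationale are at stake, not the feasibility indices in Section 2.1.

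**Working it through.** **1. Reproduce the stated dose.** The 23 ratios in Table 2 sum to 200 and the 23 doses sum to 10,000 mg, and every row's dose matches its ratio. Licorice: 20/200 × 10,000 mg = 1000 mg/day. The figure is consistent with the rest of the table and does not look like a typing slip. Over 42 days it amounts to 42 g.

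**2. Compare each herb with the level cited in Section 1.3.**

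| Herb | Table 2 dose | Level in Section 1.3 | Ratio |
|---|---|---|---|
| Licorice | 1000 mg | >600 mg | 1000/600 = 1.67 |
| Dong quai | 500 mg | 4500 mg | 500/4500 = 0.11 |
| Ginseng | 350 mg | >2000 mg | 350/2000 = 0.175 |

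The formula is below the cited level for two of the three herbs and above it for licorice.

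**3. Allow for missed doses.** At the 66% adherence threshold of Section 2.1, mean intake is 0.66 × 1000 = 660 mg/day, still above 600. Intake falls to 600 mg/day or less only at adherence of 600/1000 = 60% or lower.

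**4. Test the assumption about basis.** Let k be the strength, per mg, of the material behind the 600 mg figure relative to the Table 2 material. The documents do not give k. The adjusted ratio is 1000/(600 × k).

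- k = 1 (same basis): 1.67.
- k = 1.67: 1.00, so the excess is gone.
- k = (2000/350) × (1000/600) = 9.5: 0.175, the margin that ginseng has.
- k below 1: the ratio is above 1.67.

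**5. Look for a potassium requirement.** None of the 7 exclusion criteria, 6 withdrawal reasons or 16 rows of Table 3 names potassium. The liver tests are also missing from the blood row, but exclusion 4 and withdrawal reason 5 imply them. Nothing implies potassium in the same way.

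**6. Ask how far standard of care reaches.** The blood row is marked at all five visits, but Section 7.0 counts only 2 of the 5 as standard of care. Inclusion criterion 6 also admits patients with no chemotherapy due in the coming six weeks. Neither the timing nor the content of routine blood tests can therefore be taken as uniform.

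**7. Gauge the likely number of cases.** If a 1% rate applied to each patient, the expected number in 15 would be 15 × 0.01 = 0.15, and the chance of at least one would be 1 − 0.99^15 = 0.14. Both are upper figures for a rate below 1%. Section 1.3 attaches that rate to reported side effects. It gives no rate for changes in potassium without symptoms.

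**The case against.** The strongest reply is that the conflict rests on an unstated basis. Table 2 lists a prepared root, while Section 1.3 says only licorice and relies on an outside source. Section 1.4 sends the reader to Appendix 3 for more detail on the herbs. That appendix was not supplied, and it could state the basis and settle the matter. This stands, and it is why the conclusion is conditional.

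Second, Section 1.4 speaks of some mild side effects. A reader might infer that it places every reported effect at far higher doses, but it does not say so. The closer conflict is between Section 1.3 and Table 2. This stands too.

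Third, a test that is not named may still be done. Blood is scheduled at every visit, the row names no analytes at all, and usual care may well include potassium. A reader might infer that potassium will go unmeasured. The documents show only that nothing requires it.

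Fourth, the hazard is disclosed in Section 1.3 and safeguards exist: symptom review with CTCAE grading (Section 5.2), and withdrawal on the doctor's suspicion of a side effect or for an adverse reaction (Section 4.5, reasons 2 and 3). These could act on a low potassium value once it is known, so a dedicated withdrawal reason is not needed. They do not produce the value.

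Finally, the protocol calls the effect rare. That tempers the urgency, but the label belongs to doses that Section 1.3 calls very high, and by its own example the study dose of licorice is among them.

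**Conclusion.** The point holds in a limited form. As written, the study dose of licorice is 1.67 times the level that the protocol cites for hypertension and hypokalemia, for a duration within the range it cites. The label of very high doses in Section 1.3 and the remark on dose in Section 1.4 therefore do not fit this herb. The size depends on both figures sharing a basis: the excess disappears if the cited form is at least 1.67 times as strong as the Table 2 material. Potassium is not required anywhere in the supplied text, and standard of care alone does not guarantee it at these visits.

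A reader might go further and infer that the formula is unsafe or should be recompounded. The documents do not support that. The 600 mg figure is given as an example, the effect is called rare, the basis is open, and blood pressure is presumably followed. The point deserves correction, with moderate confidence, as a matter of safety and internal consistency. It does not change how acceptability or feasibility is assessed.

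**What to change.** 1. **Correct the rationale.** In Sections 1.3 and 1.4, say that licorice at 1000 mg/day exceeds the cited level of 600 mg/day, or state the basis (herb, extract or equivalent) on which it does not.
2. **Name potassium in the existing blood row of Table 3.** Measure it at baseline (Visit 1, or screening if the result is needed for eligibility) and at weeks 2, 4 and 6. Grade low values by CTCAE v3.0, which Section 5.2 already uses, and handle them under withdrawal reasons 2 and 3. A separate withdrawal reason is optional.

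**Cost.** The text changes are a few sentences and one named analyte. The testing is 15 patients × 4 time points = 60 potassium results, more if screen failures are tested and fewer new ones where usual care already includes potassium. A few draws may go beyond usual care. A few extra withdrawals are possible; each would lower the completion rate by at most 1/15 = 6.7 percentage points, and by less if the patient attends the end-of-study visit that Section 4.5 still requests.

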6.0 CONFIDENTIALITY AND DATA HANDLING

6.1 Patient Confidentiality

All the information collected during the study will remain confidential within the limits of the Law. The principal investigator must assure that subjects' anonymity will be maintained and that their identities are protected from unauthorized parties. On any study documents subjects should not be identified by their names, but by a unique subject ID number (identification code). The principal investigator should keep a subject enrollment log showing codes, names and addresses. This log will be kept for the period of one year after the end of the study. None of the information collected from this register will be for research purposes and all information will be destroyed after 12 months following the end of your participation in this study. All the other study information will be kept for 25 years by the principal investigator of the study.

The study results could be printed/published in medical journals or shared with other people at scientific meetings. The study team will comply with the requirements for publication of study results.

For the purpose of monitoring this research, and research study files as well as medical records of participants could be checked by a person authorized by the Research Ethics Committee of the Jewish General Hospital. These people are obliged to respect information privacy.

